9.3 POPULATIONS FOR ANALYSES

Intent-to-Treat (ITT) Population

The ITT population will consist of all enrolled subjects regardless of whether or not they actually received ixekizumab. This sample will be used for summaries and analyses of the primary endpoint and the secondary endpoints.

Safety Analysis set

The safety analysis set will include all enrolled participants who were given at least one dose of ixekizumab, and on whom any post-dose data are available and are classified according to the treatment actually received. The safety analysis set will be used to assess safety and tolerability variables.

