5.4 SCREEN FAILURES

If the patient fails to qualify for the study after signing the informed consent form, they will be considered a screen failure. Screen failures should be recorded on the electronic screening log along with the reason for disqualification. Patients who screen fail and are not randomized will be eligible to rescreen later. Patients should only be enrolled into the study once, therefore patients who have been randomized will not be eligible for future screening.

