5.5 STRATEGIES FOR RECRUITMENT AND RETENTION

5.5.A Planned Recruitment Activities

The research strategy for the present study calls for the enrollment of up to N=20 adults (aged 18-70 years) with treatment-resistant depression over the two-year project period. Our total enrollment target of up to N=20 reflects individuals who are screened, eligible, and treated in the protocol. Anticipating screen fails, dropouts after enrollment and lost to follow-ups post-treatment, we plan to screen a total of N=40 individuals over the proposed 24-month recruitment period. This enrollment period provides for a highly feasible **~2 subjects screened and ~1 subject who complete baseline visits per month**, allowing for 2-month follow-up after the enrollment of last subject.

DAC has implemented a robust workflow for identifying and screening candidates for clinical research and employs direct-to-patient advertising through radio, newspaper, internet-based and other media outlets. A centralized programmatic intake process (under protocol **STUDY-10-00606; A Screening Protocol for Adult Patients with Mood and Anxiety Disorders, Chronic Medical Conditions, and Healthy Volunteers.**) is employed that includes a central phone line, a program-specific email, and a website featuring a web-based survey that patients can take to see if they qualify for studies. Individuals who contact DAC by completing the pre-screener online survey are automatically entered into a secure web-based database in order to be contacted by a member of the research staff for additional screening.

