6.3 MEASURES TO MINIMIZE BIAS: RANDOMIZATION AND BLINDING

6.3.1 RANDOMIZATION AND BLINDING

This study will be open-label with one treatment condition. Given that this study is open label with one treatment condition, participants cannot be blinded.

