8.2 EVALUATIONS BY VISIT

SCREENING VISIT (V0, WEEK -4 – 0)

1. Review the study with the subject and obtain written informed consent and HIPAA authorization.
2. Review inclusion and exclusion criteria.
3. Assign the subject a unique screening number.
4. Record demographics data.
5. Record medical, psychiatric, family, medication and treatment history, diagnosis date, and prior treatments.
6. Record concomitant medications.
7. Perform self and clinician administered ratings scale:

- SCID-5-RV
- CGI-S
- CSSR-S – Past month
- QIDS-C

8. Perform a complete physical examination.
9. Perform and record vital signs.
10. Urine for urinalysis, urine toxicology and pregnancy test (female subjects who are of childbearing age).
11. Collect blood for clinical laboratory tests.
12. Schedule subject for Baseline (Visit 1) within 4 weeks of Screening.

Note: The screening visit may occur on up to three separate days. The whole procedures will be completed before the treatment day and within four weeks of the first screening visit. Screening measures may be completed under a separate screening protocol at each site. As long as the assessments are completed within four weeks of the signing of consent for this protocol, the screening measures will not be repeated. Subjects who are deemed screen fails may be re-screened at a later date, based on PI discretion. If re-screened, subjects will repeat all screening procedures.

A portion of this visit, including clinician administered rating scales, may be completed remotely via a HIPAA-compliant virtual platform.

BASELINE (V1, WEEK 0)

1. Obtain interval medical history.
2. Record any AEs.
3. Record changes to concomitant medications.
4. Collect urine for urine toxicology and pregnancy test (female subjects who are of childbearing age).
5. Record vital signs
6. Perform self and clinician administered ratings scale:
 - MADRS
 - CSSRS-Since Last Visit
 - HAM-A
 - CGI-S
 - CGI-I
 - SHAPS
 - TEPS
 - QIDS-SR
7. Neuroimaging procedures.
8. Collect blood immunological measures.
9. Dispense study medication.

Note: The Baseline Visit should take place within four-weeks of the date that the subject signed consent for this study. The Baseline Visit may occur on up to two separate days within 5 business days of each other. The neuroimaging procedures must be completed before the subject is randomized and receives

the study drug.

VISIT 2 (WEEK 2)

1. Obtain interval medical history.
2. Record vital signs
3. Record any AEs.

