9.2 SAMPLE SIZE DETERMINATION

In this study, up to 20 patients will be enrolled. We anticipate 80% of more of the sample will complete treatment (<20% early drop out) and the treatment will be well-tolerated with no treatment-related adverse effects. A sample size of 20 patients will produce a two-sided 95% confidence interval around the proportion who completed treatment with a width equal to 0.35 when the sample proportion is 0.8. Precision was estimated using PASS 2019 (26).

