9.4.2 ANALYSIS OF THE PRIMARY EFFICACY ENDPOINT(S)

The primary efficacy endpoint is the completion of treatment measured by the receipt of all three ixekizumab injections (160 mg at week 0, 80 mg at weeks 2 and 4) to assess the safety and feasibility of ixekizumab in patients with TRD. The analysis of the primary endpoint for this study will be descriptive. The proportion of enrolled patients that complete treatment and the corresponding 95% confidence interval will be reported.

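### Does the lack of a defined enrollment event leave the denominator of the primary completion rate open?

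*Combined protocol and SAP*

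**What the plan says.** Section 9.4.2 states the primary analysis: "The proportion of enrolled patients that complete treatment and the corresponding 95% confidence interval will be reported". Section 9.3 gives the population for it: "The ITT population will consist of all enrolled subjects regardless of whether or not they actually received ixekizumab". Section 9.2 caps enrollment at 20, gives a two-sided 95% interval of width 0.35 at a sample proportion of 0.8, and treats drop-out as a share of that sample: "We anticipate 80% of more of the sample will complete treatment (<20% early drop out".

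Four other places bear on who is enrolled.

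- Section 5.4, on rescreening: "Patients should only be enrolled into the study once, therefore patients who have been randomized will not be eligible for future screening".
- Section 8.2, in the note to the Baseline visit: "The neuroimaging procedures must be completed before the subject is randomized and receives" study drug.
- Section 6.3.1, on the design: "This study will be open-label with one treatment condition".
- Section 5.5.A, on recruitment: "Our total enrollment target of up to N=20 reflects individuals who are screened, eligible, and treated in the protocol", followed by "Anticipating screen fails, dropouts after enrollment and lost to follow-ups post-treatment, we plan to screen a total of N=40 individuals".

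Section 9.1 says that the primary analysis is descriptive, without a formal test. No section mentions replacing patients who drop out.

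**The concern.** The endpoint is completion, so the patients who are hardest to classify are the ones it is meant to count. The denominator rests on one word, enrolled, and three features of the text make that word look unstable.

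1. Section 5.4 links enrollment to randomization and Section 8.2 places randomization at baseline. With one open-label condition that step never happens.
2. Section 5.5.A says the 20 are treated patients, whereas Section 9.3 keeps enrolled patients who were never dosed.
3. Section 5.5.A gives post-enrollment losses as one reason to screen 40. This can be read as putting those losses outside the 20, while Section 9.2 puts them inside.

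If the denominator could be chosen after the losses were known, the reported rate could move by several points per patient. The rate is a feasibility figure, and Sections 2.1 and 4.2 say the results are to inform larger trials.

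**Working it through.** **Inputs.** Up to 20 enrolled and an anticipated completion proportion of 0.8 (Section 9.2), so 0.8 × 20 = 16 completers. The documents give no count of patients lost before the first dose; one and two are assumed for illustration.

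**Step 1: the plan's own figure.** The normal-approximation width is 2 × 1.96 × √(0.8 × 0.2 / 20) = 0.351, which matches the stated 0.35. That figure holds with all 20 enrolled patients in the denominator and drop-outs among them.

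**Step 2: what Section 9 fixes.** Section 9.3 expressly allows for people who are enrolled but undosed, so enrollment must come before the first dose. Section 5.4 makes anyone who signs consent and then fails to qualify a screen failure, so enrollment must come after eligibility is established. The only interval left unclear runs from confirmed eligibility to first dose. It is short. Section 8.2 asks for baseline within four weeks of consent, allows baseline to be split over at most two days within 5 business days, and ends that visit with dispensing of study drug.

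**Step 3: size of what is left.** Exact (Clopper-Pearson) 95% limits for x completers of n are the 0.025 quantile of Beta(x, n−x+1) and the 0.975 quantile of Beta(x+1, n−x).

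| Reading (16 completers) | Proportion | Exact 95% interval |
|---|---|---|
| All 20 enrolled (Section 9.3) | 16/20 = 80% | 56% to 94% |
| Treated only, one of the 20 undosed | 16/19 = 84% | 60% to 97% |
| Treated only, two of the 20 undosed | 16/18 = 89% | 65% to 99% |

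With nobody undosed, the readings agree.

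**Step 4: drop-outs after the first dose.** Under Section 5.5.A the 20 are treated patients. A patient who is dosed at Week 0 and then leaves has been treated and is inside the 20, as in Section 9.2. A patient lost after treatment is inside for the same reason, and is a completer if all three doses were given. The recruitment figures fit this reading. Screening 40 for 20 is 40/20 = 2 to 1, and Section 5.5.A's monthly rates are about 2 screened to about 1 completing baseline, also 2 to 1. On these rounded rates the planned loss falls before treatment, with no evident pool of replacements.

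**Step 5: replacement.** Suppose 4 of the first 20 dropped out, 4 more were enrolled and 3 of those completed. Completers would be 16 + 3 = 19 and enrolled 20 + 4 = 24. Sections 9.3 and 9.4.2 then require 19/24 = 79% (58% to 93%), hardly different from 80%. The alarming figure, 19/20 = 95%, divides completers drawn from 24 enrolled patients by 20. Section 9 does not allow that.

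**The case for a change.** The strongest case for a change is the clash between treated in Section 5.5.A and the express inclusion of undosed patients in Section 9.3. The gap can arise in practice: pregnancy and urine toxicology tests are repeated at baseline and imaging comes before dosing, so a patient can pass screening, attend and leave undosed. If recruitment ran until 20 were treated and the undosed were extra, 16 completers would give 16/21 = 76% (53% to 92%) with one extra patient or 16/22 = 73% (50% to 89%) with two. In a sample this small one patient moves the rate by about 4 to 5 points, and a single sentence would settle the matter.

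Part of this stands. The enrollment event is not written down, randomization is the wrong word in Sections 5.4 and 8.2, and treated is loose. But 21 or 22 enrolled would exceed the cap of 20 in Section 9.2, and even then Section 9.3 says how to count: every enrolled patient stays in the denominator. Section 5.4 governs rescreening and Section 5.5.A governs recruitment; neither defines an analysis set. The written definition would keep the Section 9.3 denominator, so it would improve the text without altering the analysis. The facts needed to show both denominators will be recorded in any case. Section 6.4 accounts for drug dispensed to each subject, and Section 5.5.B codes the date and reason of early termination.

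**Conclusion.** The concern does not call for a change to the plan. The references to randomization are a clerical slip in a trial with one open-label condition. The missing enrollment event is a gap that analysts can fill from Sections 5.4 and 9.3: after eligibility, before first dose. The claim that drop-outs are counted outside the 20 is not supported, because a patient dosed once is already within them and no replacement is planned.

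What remains is confined to patients lost between eligibility and first dose. On an assumed one or two such patients, with 20 enrolled and 16 completers, the choice is between 80% and 84% or 89%. Both alternatives lie inside the 56% to 94% interval, and Section 9.3 already selects 80%. There is no test and no completion threshold, so no formal decision turns on the difference. This conclusion assumes that Section 9.3 is followed as written and that enrollment stays within the cap of 20.

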9.4 STATISTICAL ANALYSES

9.4.1 GENERAL APPROACH

Continuous variables will be summarized using the following descriptive statistics: number of non-missing values, means, standard deviations, medians, interquartile range, maximum, and minimum. Categorical variables will be summarized using number of non-missing values, counts and percentages.

Rates of events will be calculated as the ratio of the total number of events recorded divided by the total patient-time. Total patient-time will be calculated by summing the time (in study time units, e.g., days or months) that patients were at risk for a specific event from the reference time point until either study exit or the end of the time period of interest. Rates and their 95% confidence intervals will be reported.

Time-to-event variables will be summarized using the Kaplan-Meier method.

For any variable measured at multiple points in time, change from baseline will be calculated as the difference between the value of the variable at a specific point in time (e.g. 6 weeks) minus the baseline value. Relative change from baseline will be calculated as the value of a parameter at a specific point in

time minus the baseline value of the parameter divided by the baseline value of the parameter. Percent change will be calculated as the relative change multiplied by 100.

All hypothesis testing will be conducted at the 0.05 two-sided significance level unless otherwise specified. P-values will be rounded to three decimal places. P-values less than 0.001 will be reported as <0.001 in tables. P-values greater than 0.999 will be reported as >0.999.

Should any of the statistical methods proposed prove unsuitable during data analysis, more appropriate methods will be used. These include data transformation (for example to a logarithmic scale) to satisfy model assumptions such as normally distributed residuals with constant variance, the application of non-parametric techniques or the use of a different link function or modeling technique. The SAP will be updated with the methods used and the justification for the change prior to data set and database lock.

9.4.2 ANALYSIS OF THE PRIMARY EFFICACY ENDPOINT(S)

The primary efficacy endpoint is the completion of treatment measured by the receipt of all three ixekizumab injections (160 mg at week 0, 80 mg at weeks 2 and 4) to assess the safety and feasibility of ixekizumab in patients with TRD. The analysis of the primary endpoint for this study will be descriptive. The proportion of enrolled patients that complete treatment and the corresponding 95% confidence interval will be reported.

9.4.3 ANALYSIS OF THE SECONDARY ENDPOINT(S)

1) Baseline-to-week-6 changes in depression severity, measured by MADRS scores

MADRS scores will be reported descriptively at each time point using the number observed, mean, standard deviation, median, and interquartile range. Individual patient trajectories will be plotted over time to explore patterns in treatment response. Mean change in MADRS scores from baseline and corresponding 95% confidence intervals will also be reported at each time point.

2) Response and remission rates at week 6

The number and proportion of patients who respond to treatment and who remain in remission will be reported at each time point.

3) Baseline-to-week 6 changes in other clinical symptoms as measured by CGI-S, CGI-I, QIDS-SR, C-SSRS, SHAPS, TEPS, and HAM-A.

4) Baseline-to-week-6 changes in RSFC as evaluated by fMRI scans and changes in BBB permeability

RSFC and BBB permeability will be analyzed in the same manner described above for MADRS scores.

5) Baseline-to-week-6 changes in blood-based immune markers, including CRP and other immune markers

Biomarkers will be analyzed in the same manner described for MADRS scores above.

6) the relationship between baseline-to-week-6 changes in blood-based immune markers and RSFC and BBB permeability with changes in depression severity scores.

We will explore whether improving depressive symptoms correlate with changes in blood-based immune markers and RSFC and BBB permeability. MADRS scores will be plotted with biomarkers, RSFC, and BBB over time to evaluate trends descriptively. Fixed and mixed effects regression models may also be explored to estimate associations and 95% confidence intervals.

9.4.4 SAFETY ANALYSES

All safety analyses will be conducted in the safety population.

Safety and tolerability data will also be summarized descriptively. Adverse events will be categorized using the Medical Dictionary for Regulatory Activities (MedDRA) system organ class and preferred terms. For each group, number and rates of events and number and percent of patients will be tabulated by preferred term and system organ class.

All laboratory test results, vital signs, weight, and BMI will be summarized using descriptive statistics at each visit for raw numbers and change from baseline. Suicidality measures based on the C-SSRS will be summarized for each treatment group using descriptive statistics at each assessment.

9.4.5 BASELINE DESCRIPTIVE STATISTICS

Baseline characteristics will be reported descriptively. Continuous variables will be summarized using the number of non-missing values, means, standard deviations, medians, interquartile range, maximum, and minimum. Categorical variables will be summarized using number of non-missing values, counts and percentages.

9.4.6 PLANNED INTERIM ANALYSES

No interim analyses are planned.

9.4.7 SUB-GROUP ANALYSES

No sub-group analyses are planned.

9.4.8 TABULATION OF INDIVIDUAL PARTICIPANT DATA

Per NIMH policy, we will submit a final deidentified data set, listed by measure and time point, as part of the data sharing plan.

9.4.9 EXPLORATORY ANALYSES

Treatment effects on R-fMRI data will be explored. It is hypothesized that Ixekizumab will result in neuroimaging changes in resting state functional connectivity, and blood brain barrier permeability, evaluated with magnetic resonance imaging (MRI) scans. As there are a number of serious, potential confounders to the analysis of R-fMRI, advanced processing and analytic methods will be employed, including the use of robust artifact detection and removal (Pruim et al., 2015). We will conduct targeted analysis to explore whether treatment alters connectivity and network patterns with known abnormalities and that are specifically impacted by our treatment (e.g., fronto-striatal connectivity implicated in reward; see Heller et al., 2013).

10 SUPPORTING DOCUMENTATION AND OPERATIONAL CONSIDERATIONS

10.1 REGULATORY, ETHICAL, AND STUDY OVERSIGHT CONSIDERATIONS

10.1.1 INFORMED CONSENT PROCESS

10.1.1.1 CONSENT/ASSENT AND OTHER INFORMATIONAL DOCUMENTS PROVIDED TO PARTICIPANTS

Consent forms describing in detail the study intervention, study procedures, and risks are given to the participant and written documentation of informed consent is required prior to starting intervention/administering study intervention. The consent materials are submitted with this protocol.

10.1.1.2 CONSENT PROCEDURES AND DOCUMENTATION

Informed consent will be obtained in accordance with the Declaration of Helsinki, ICH GCP, US Code of Federal Regulations for Protection of Human Subjects (21 CFR 50.25[a,b], CFR 50.27, and CFR Part 56, Subpart A), the Health Insurance Portability and Accountability Act (HIPAA), and local regulations.

The Investigator-sponsor will prepare the informed consent form, assent and HIPAA authorization. The consent form generated by the Investigator must be approved by the IRB. The written consent document will embody the elements of informed consent as described in the International Conference on Harmonisation and will also comply with local regulations.

A properly executed, written, informed consent will be obtained from each subject prior to entering the subject into the trial. Information should be given in both oral and written form and subjects must be given ample opportunity to inquire about details of the study. If appropriate and required by the local IRB, assent from the subject will also be obtained. If a subject is unable to sign the informed consent form (ICF) and the HIPAA authorization, a legal representative may sign for the subject. A copy of the signed consent form (and assent) will be given to the subject and the original will be maintained with the subject's records.

10.1.2 STUDY DISCONTINUATION AND CLOSURE

This study may be temporarily suspended or prematurely terminated if there is sufficient reasonable cause. Written notification, documenting the reason for study suspension or termination, will be

provided by the suspending or terminating party to study participants, investigator, funding agency, the Investigational New Drug (IND) sponsor and regulatory authorities. If the study is prematurely terminated or suspended, the Principal Investigator (PI) will promptly inform study participants, the Institutional Review Board (IRB), and sponsor and will provide the reason(s) for the termination or suspension. Study participants will be contacted, as applicable, and be informed of changes to study visit schedule.

Circumstances that may warrant termination or suspension include, but are not limited to:

- Determination of unexpected, significant, or unacceptable risk to participants
- Demonstration of efficacy that would warrant stopping
- Insufficient compliance to protocol requirements
- Data that are not sufficiently complete and/or evaluable
- Determination that the primary endpoint has been met
- Determination of futility

Study may resume once concerns about safety, protocol compliance, and data quality are addressed, and satisfy the sponsor, IRB and/or Food and Drug Administration (FDA).

10.1.3 CONFIDENTIALITY AND PRIVACY

Participant confidentiality and privacy is strictly held in trust by the participating investigators, their staff, and the sponsor(s) and their interventions. This confidentiality is extended to cover testing of biological samples and genetic tests in addition to the clinical information relating to participants. Therefore, the study protocol, documentation, data, and all other information generated will be held in strict confidence. No information concerning the study or the data will be released to any unauthorized third party without prior written approval of the sponsor.

All research activities will be conducted in as private a setting as possible.

The study monitor, other authorized representatives of the sponsor, representatives of the Institutional Review Board (IRB), regulatory agencies or pharmaceutical company supplying study product may inspect all documents and records required to be maintained by the investigator, including but not limited to, medical records (office, clinic, or hospital) and pharmacy records for the participants in this study. The clinical study site will permit access to such records.

The study participant's contact information will be securely stored at each clinical site for internal use during the study. At the end of the study, all records will continue to be kept in a secure location for as long a period as dictated by the reviewing IRB, Institutional policies, or sponsor requirements.

Certificate of Confidentiality

To further protect the privacy of study participants, a Certificate of Confidentiality will be issued by the National Institutes of Health (NIH). This certificate protects identifiable research information from forced disclosure. It allows the investigator and others who have access to research records to refuse to disclose identifying information on research participation in any civil, criminal, administrative, legislative,

or other proceeding, whether at the federal, state, or local level. By protecting researchers and institutions from being compelled to disclose information that would identify research participants, Certificates of Confidentiality help achieve the research objectives and promote participation in studies by helping assure confidentiality and privacy to participants.

